## RISKS TO HUMAN SUBJECTS

### ***a. Human Subjects Involvement, Characteristics, and Design***

The collaborating sites are the UTHSCSA, the University of Louisville and the University of Cincinnati. Under the direction of [name], Biomedical Development Corporation will create an identical set of study binders containing source documents and case report forms for each of the study sites. Each site will have a designated study coordinator who will be responsible for obtaining, managing and protecting the data. All study materials will be kept under lock and key. The study sites will be monitored throughout the project period by BDC for study compliance, including a preliminary monitoring visit prior to the initiation of the trial to ensure that the study site is adequately equipped and staffed to perform the trial.

The Federal Wide Assurance number for the UTHSCSA is FWA00005928. The Assurance of Compliance number for the UTHSCSA is IRB00000553. The Federal Wide Assurance number for the University of Louisville is FWA00002211. The Federal Wide Assurance number for the University of Cincinnati is 00003152. The Federal Wide Assurance number for Biomedical Development Corporation is FWA0000749.

### ***b. Sources of Materials***

- Individuals enrolled into the study will be assigned study password-protected ID numbers.
- All information obtained from human volunteers will be utilized strictly for research purposes.

UTHSCSA tracking number: HSC20150321H

Information to be collected includes: demographic data, MINI-6.0, self-reported symptoms via the KTABS or eMoods (i.e., online questionnaire), Life Functioning Questionnaire, BISS and subjective information regarding the user experience with the software.

- Information will be collected, handled and stored according to the HIPPA regulations and study participants will be asked to read a Privacy Notice and sign a Research Authorization (HIPPA consent). Study participants will be given a copy of the signed consent form for his/her records.

### ***c. Potential Risks***

- There are only minimal risks associated with participation in this study. There is no intervention component in the trial. None of the planned activities are likely to be stressful to the subjects. However, it is possible that a subject could worsen in a time frame between clinic treatment visits. We will convey the evidence of the person's worsening to his/her psychiatrist or other therapist.

### ***d. Adequacy of Protection Against Risks***

#### **Recruitment and Informed Consent**

- Participants will be individually recruited from the respective study sites. The methods of this research as well as the Informed Consent Document and all recruiting materials will be approved by the Institutional Review Boards at the UTHSCSA, University of Louisville, and the University of Cincinnati, respectively.
- Study volunteers will have a detailed discussion of the study requirements and procedures with Drs. [name], [name], [name] or the study coordinator at the respective sites. All information regarding the study procedures will be provided to the subjects in understandable layman terms on an IRB approved informed consent form. Participants will receive up to \$600 for participation (Baseline visit, Weeks 8, 16, 24, 32, 40, and 52 at \$10/appointment plus the 52 weekly activities at \$10/self-assessment) for a total of up to \$600. Focus group participants will be compensated for their participation with a \$20 local state voucher.

At the UT Health Science Center, payment for study related procedures will be paid through use of the Mastercard. Compensation will be automatically credited after completion of each study visit. Name, address and date of birth will be shared with a third-party solely for the purposes of compensation processing. This information will only be used for the administration of the compensation (ClinCard) and will be kept strictly confidential.

In addition to the compensation on the card, the participant may also elect to receive study-related messages (text and/or email).

### ***e. Protections Against Risk***

Minimal risk to subjects or subject's privacy is anticipated. Nonetheless, we recognize the need for strict protection of confidentiality in this study. To address this, records of patients will be retained as required by statute in locked files. All computer files will be password protected. Subjects will be identified in common-use computer files by ID number only. Research reports and publications will report only group data and not individual names. Identities of subjects will not be revealed in the publication or presentation of any results from this project. All investigators and research staff at the respective institutions have completed the requirements for human research subjects' protection. All investigators and research staff at BDC have completed the requirements for human subjects' protection. The study will be performed in accordance with HIPPA regulations and approved by the IRBs at the UTHSCSA, the University of Louisville and the University of Cincinnati.

Participation in the study will be terminated if a patient has a score of 4 on the BISS suicide item, BISS Depression Scale  $\geq 50$ , or BISS Mania Scale  $\geq 35$ , or if the treating psychiatrist determines that a patient poses an imminent risk of self-harm.

All subjects enrolled in the trial will have been under care of a psychiatrist at their respective institutions prior to enrolling in the study. All subjects will continue to receive evidence-based care provided by outstanding psychiatrists at the three sites. Participation in the study will not impact the patient's routine clinical care for his/her bipolar condition. The study's planned visits will generally be scheduled to coincide with the patient's regularly scheduled clinic visits both for convenience and in order to not interfere with regular care.

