#### **The clinical trial will:**

- a. Assess aggregate time spent in seven primary clinical states of BD (remitted; subsyndromal depression, mania or mixed state; and syndromal depression, mania or mixed state).
- b. Assess the weekly completion of KIOS-Bipolar and eMoods.
- c. Determine indices of patient satisfaction with the format, ease of use, time required and patient motivation for continuing use of the patient tools both during the trial and following completion.
- d. Determine patient satisfaction with the clinical information on BD illness trajectory and recommendations to facilitate good health and effective interventions. Note that eMoods does not provide this element of information, therefore no comparative data will be feasible for this one objective.
- e. Assess patient scored life function indices (Life Function Questionnaire (LFQ) over the 52 week period of the study.
- f. Assess the relationship between the 8 symptom items in K-B with relevant items rated both by clinicians and as self-assessments by patients at seven time points (week 0, 8, 16, 24, 32, 40 and 52) in the study. These are times at which clinical care visits will routinely occur, and therefore will not add either to extra burden on the participants, or extra contact time with staff. Subjects randomized to eMoods will be similarly scheduled, with the correlations limited to those feasible with the eMoods product. Self-assessments with the 27 item BISS-Self are routinely obtained as part of regular treatment visits.

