**Table 1. Schema for Randomized Clinical Trial**

Week	0	1-7	8	9-15	16	17-51	24, 32, 40	52	RS
MINI-6.0, Demographics/course of illness	X								
K-TABS/eMoods	X	X	X	X	X	X		X	
Life Functioning Questionnaire	X		X		X			X	
BISS-42,	X		X		X		X	X	
BISS Self-Assessment	X		X		X		X	X	X
KIOS NIH Software Evaluation Form					X			X	

The clinician administered scale will be the 42 item Bipolar Inventory of Symptoms Scale (BISS), however comparisons will be limited to the symptom areas represented in both K-B and eMoods, e.g., depression and mania subscales; depression, mania, irritability and anxiety domains. The BISS Self (BISS-S) is a 27item scale covering similar symptoms to the BISS, but answered as yes/no, rather than the 0-4 range of the BISS. The MINI is a structured diagnostic interview providing current and lifetime psychiatric diagnoses, requiring approximately 20 minutes.

g. Estimate the utility of ancillary features of Kios-Bipolar or eMoods. These features include capability to submit to the investigative staff displays of symptom trajectories for the patient's medical record and visual displays of selected aspects of the patient's illness/wellness. No transmission of data to treating clinical staff will occur as component of this study.

h. Assess sensitivity of K-B assessed improvement or worsening by comparison with assessment by BISS-Self and BISS-42.

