**Inclusion Criteria:**

1. Male or female outpatients 18 years of age or older
2. Bipolar I or II disorder as assessed by MINI 6.0
3. In psychiatric outpatient treatment at UTHSCSA, University of Louisville, or Lindner Center of Hope, Mason Ohio
4. Currently taking mood stabilizer or second generation antipsychotic for 4 weeks or longer
5. Ability to access Kios-Bipolar or eMoods (via computer, smartphone or tablet)

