**Exclusion Criteria:**

1. Unwilling or unable to comply with study requirements
2. Drug/alcohol dependence within the past 30 days

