**Early termination:**

Participation in the study will be terminated if a patient has a score of 4 on the BISS suicide item, BISS-Depression Scale  $\geq 50$ , or BISS Mania Scale  $\geq 35$  for 4 consecutive weeks, or if the treating psychiatrist determines that a patient poses an imminent risk of self-harm.

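### Entry and termination rules conflict at baseline: eligibility has no severity limit, the BISS-42 is rated at week 0, and two sections disagree on when a BISS score ends participation

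*Combined protocol and SAP*

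**What the plan says.** **Entry.** The Inclusion Criteria ask for adult outpatients at the three sites who can access one of the tools, with "Bipolar I or II disorder as assessed by MINI 6.0" and "Currently taking mood stabilizer or second generation antipsychotic for 4 weeks or longer". There are two Exclusion Criteria: "Unwilling or unable to comply with study requirements" and "Drug/alcohol dependence within the past 30 days". Neither list mentions the BISS depression scale, the BISS mania scale or suicidality.

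**Termination, two versions.** Section e, Protections Against Risk, says: "Participation in the study will be terminated if a patient has a score of 4 on the BISS suicide item". It goes on to a depression score of at least 50, a mania score of at least 35, or the psychiatrist's judgement of self-harm risk. It gives no duration. The Early termination section lists the same three BISS criteria, then continues "for 4 consecutive weeks, or if the treating psychiatrist determines that a patient poses an imminent risk of self-harm".

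**Schedule.** Item f under The clinical trial will places the clinician and self ratings "at seven time points (week 0, 8, 16, 24, 32, 40 and 52) in the study". Table 1 agrees for the BISS-42 and also marks first use of the assigned tool at week 0. No screening visit is described, and the order of randomisation and the week-0 BISS-42 is not stated.

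**Analysis.** The Plan of analysis makes adherence and attrition the primary aims. It sizes the study on 90 subjects, allowing up to 30 of the 120 enrolled to meet a criterion for early termination.

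**The concern.** The scale that can end participation is rated at the visit where participation begins, and nothing in the eligibility criteria refers to it. Under section e, a person rated at a cut-off at week 0 is eligible and also meets a termination criterion. The Early termination section may or may not say the same, depending on how its duration is read. Staff seeing a severely ill or suicidal person at baseline therefore have two rules that do not agree.

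The statistical stake is what attrition means. A baseline termination reflects the state in which a person arrived and says nothing about willingness to keep using KIOS-Bipolar or eMoods. Hypothesis b counts completion of the 52-week protocol as part of persistence, so such a person would be a non-completer. The plan does not separate protocol-mandated endings from voluntary dropout.

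**Working it through.** **1. The two termination rules at a single week-0 rating.** The four-week phrase in the Early termination section follows the mania criterion, so it can be read as attaching to mania only or to all three.

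| BISS criterion met at week 0 | Section e | Early termination, duration on mania only | Early termination, duration on all three |
|---|---|---|---|
| Suicide item 4 | ends | ends | does not end |
| Depression ≥50 | ends | ends | does not end |
| Mania ≥35 | ends | does not end | does not end |

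The sections disagree on at least one row under either reading. Week-0 termination on a BISS score is possible under section e and under the mania-only reading. It is ruled out only under the reading that applies the duration to all three.

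**2. Can four consecutive weeks be observed?** The clinician BISS is due at weeks 0, 8, 16, 24, 32, 40 and 52. The gaps are 8, 8, 8, 8, 8 and 12 weeks, and the shortest is twice the required duration. The BISS-Self follows the same visits and is answered yes/no, so it cannot give an item score of 4. The weekly KIOS-Bipolar questions in Table 2 are eight items with none on suicide. No unscheduled clinician ratings are described. The duration cannot be verified on the stated schedule.

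**3. The plan's own power figure.** Inputs from the Plan of analysis: n = 90, 0.65 against 0.5, two-sided 0.05, stated power 0.80. With the null variance for the critical value and the alternative variance for power:

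- null SE = √(0.25/90) = 0.0527; alternative SE = √(0.65 × 0.35/90) = 0.0503
- power = Φ[(0.15 − 1.96 × 0.0527)/0.0503] = 0.824

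Using the null variance throughout gives 0.812, and the exact binomial test (critical count 55 of 90) also gives 0.812. The stated 0.80 is reproduced. The allowance also checks: 120 − 30 = 90, and 30/120 = 25%.

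**4. How much week-0 terminations could matter.** The documents give no baseline BISS distribution. The share q below is an assumption, shown as a range that includes zero.

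| q | Ended at week 0 (120q) | Later loss that still leaves 90: (30 − 120q)/(120 − 120q) | n if 25% of the rest are also lost: 0.75 × (120 − 120q) | Power at that n |
|---|---|---|---|---|
| 0% | 0 | 25.0% | 90 | 0.824 |
| 2% | 2.4 | 23.5% | 88.2 | 0.816 |
| 5% | 6 | 21.1% | 85.5 | 0.803 |
| 10% | 12 | 16.7% | 81 | 0.781 |
| 15% | 18 | 11.8% | 76.5 | 0.757 |

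If these cases fall within the 30, n stays at 90 and power is unchanged. If they come on top of a 25% later loss, power stays above the stated 0.80 at q = 5% and is about two points below it at 10%. The overall attrition rate carries q directly: at 5%, five percentage points of attrition would owe nothing to either tool.

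**The case against.** The strongest reply is that the Early termination section is the dedicated one. If its duration covers all three criteria, no single week-0 rating can end participation. That is a fair reading, but it does not clear the plan: section e then contradicts it on every criterion, and the duration cannot be observed on the schedule.

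Second, the order of events is not stated. The MINI is also a week-0 procedure and establishes an inclusion criterion, so some checks evidently precede assignment, and the BISS-42 may be among them. This stands. A reader might infer that people will be randomised and terminated at the same visit; the documents show only that their wording permits it.

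Third, broad entry is a legitimate choice. This is an effectiveness study that tracks syndromal states, and being eligible yet later meeting a stopping rule is no contradiction. This also stands. The absence of a severity limit is not an error in itself; the gap is the unaddressed overlap at week 0.

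Fourth, the general compliance exclusion might be used for such a person, and the dropout model includes health factors. Neither settles the matter. The exclusion does not mention severity, and sites could apply it differently. The model does not name baseline BISS and does not separate mandated endings from voluntary ones.

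**Conclusion.** The point holds in a limited form. The contradiction between the two termination sections, and between the four-week duration and the BISS schedule, is plain from the text. The overlap with eligibility at week 0 follows under section e, and for the suicide and depression criteria also under the mania-only reading of the Early termination section. How many people it touches is unknown and could be near zero, since entrants are treated outpatients already under psychiatric care.

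Three stronger inferences are not supported:

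- **No data at all from such subjects.** Hypothesis d places satisfaction questionnaires shortly after discontinuation as well as completion, and a week-0 tool entry may exist. What is missing is any described clinical-state or LFQ follow-up after termination.
- **An undersized study.** The allowance of 30 is meant for people who meet a termination criterion, and the power loss is small across most of the assumed range.
- **Bias between arms.** A rating made before the tools are used should not differ systematically by arm, and nothing in the documents shows that it would.

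What remains is a matter of interpretation and consistent conduct: conflicting instructions at baseline, and an attrition measure that mixes mandated endings with voluntary dropout.

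**What to change.** 1. Reconcile the Early termination section and section e with each other, with the BISS schedule and with the eligibility criteria, including which criteria the duration applies to and how it would be observed.
2. State that the existing week-0 BISS-42 is scored before randomisation.
3. Have the investigators state how a person who already meets a criterion at that visit is handled. No cut-off or entry rule is proposed here; those are for the investigators.
4. Keep every randomised subject in the attrition and persistence analyses, and report protocol-mandated terminations separately from voluntary dropout. Attrition should not be counted only from first use of the tool: that would drop randomised people who never open it, and their non-use is itself non-persistence under hypothesis b.

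The cost is revised wording, a small change in the order of week-0 procedures, and one extra attrition category. No new assessment is needed.

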#### ***f. Potential Benefits of the Proposed Research to Human Subjects and Others***

Study participants may benefit by becoming more aware of their changing symptoms and improving their ability to manage and track their bipolar disorder.

The results of the research may yield benefits to the class of persons with bipolar disorders, whose treatment interventions, both in research studies and in routine clinical settings, may be optimized and made more effective consequent to the utilization of the K-B recommended interventions.

#### **IMPORTANCE OF THE KNOWLEDGE TO BE GAINED**

- Psychiatric investigators, health care providers and government officials have all recognized that current guideline based treatments are limited in minimally personalizing interventions based on mediating variables that dynamically occur during treatment. The potential application of more personalized and evidence based intervention strategies could reduce the functional and morbidity burdens of bipolar disorders, which are a significant U.S. public health problem.
- Subjects will be subject to only minimal risk, as the study contains no intervention component. The minimal risks of the study seem reasonable in consideration of the potential that K-TABS has to improve care of bipolar disorder and reduce healthcare utilization and costs.

#### **DATA AND SAFETY MONITORING PLAN**

This Data and Safety Monitoring Plan is intended to ensure the safety of participants in the Clinical Trial and the validity and integrity of the data and reporting. Biomedical Development Corporation (BDC) maintains a chartered Independent Data and Safety Monitoring Board (DSMB) that will review the study prior to initiation. BDC is the sponsor for the Clinical Trial and also serves the role of data coordinator. The Clinical Trial is to be performed in compliance within the guidelines of the National Institutes of Health (NIH) and the IRBs of the UTHSCSA, University of Louisville, and the University of Cincinnati. The Principal Investigator of the Clinical Trial (PI) is [name].

#### **Monitoring the progress of the Clinical Trial**

##### **Responsibilities for Monitoring the Clinical Trial follow:**

1. The PI is responsible for continuously monitoring the conduct of the trial and is the primary individual charged with identification and reporting of all AE and SAE occurrences.

UTHSCSA tracking number: HSC20150321H

2. On site monitoring is also conducted by the Regulatory Manager at BDC who provides systematic monitoring for the following central elements: protocol eligibility (direct source documentation of eligibility as defined in the protocol), appropriateness of consent documentation, and timeliness and accuracy of data, including the timeliness of reporting adverse events and serious adverse events. Monitoring for central elements will be performed on all subjects. Reports to BDC documenting the central elements are generated at six month intervals. Other monitoring reports are generated as needed or requested.
  
3. Assuring Compliance with Requirements for Reporting Adverse Events: All adverse events (AE) and serious adverse event (SAE) forms are submitted by the PI directly to the IRB and BDC. BDC is responsible for submitting AE and SAE reports as required to the DSMB and NIH including OHRP.

### **Monitoring by the Data and Safety Monitoring Board (DSMB)**

The DSMB includes a minimum of four recognized clinical investigators and two or more representatives from the Sponsor including [name], President of BDC. The Board convenes every six months to review materials. The validity of the data is based upon the Clinical Trial infrastructure and the requirements for primary monitoring by the PI and the Regulatory Manager as summarized above. Reports of the DSMB are submitted independently to BDC and subsequently forwarded to the IRB, with a copy to the Principal Investigator.

We will endeavor to ensure that both sexes are adequately represented in the study. Based on epidemiologic studies (e.g. the Epidemiologic Catchment Area Program) and the composition of the patient population of the proposed sites, we anticipate that approximately 50% of the participants will be women.

We plan to include representatives of all minority groups in the proposed research. We have specifically included sites with demonstrated ability to recruit underrepresented minority groups and will review recruitment and enrollment efforts periodically to ensure that we are making every effort possible to enroll a representative sample. We expect to maintain or exceed 30% minority representation in the study. In particular, we expect that at least 15 % of subjects enrolled will be Hispanic and that at least 15 % will be African American.

We are including children ages 18-21. We will include only individuals 18 or older because we are not targeting a pediatric population (ages younger than 18). Additionally, the proposed sites are adult outpatient clinics and thus, the principal investigators and study staff have expertise in treating adults. We anticipate that children ages 18-21 will constitute approximately 5% of the sample.
